#### Aim 2 Hypothesis Testing Plan.

**Hypothesis 3:** Those with greater SDA will have greater AUD severity, greater LDH, greater negative urgency, greater density of familial history of alcoholism, and reduced subjective, behavioral, and electrophysiologic sensitivity to alcohol. To minimize error inflation from multiple univariate tests, we will use structural equation modeling (R3.01 data analysis software using the lavaan statistical package; Figure 6). We will examine AUD severity as an observed independent variable of AUD symptom count. Lifetime Drinking History and density of family history of alcoholism will be observed variables, computed with information collected with Concordia Lifetime Drinking Questionnaire and the SSAGA family history module. Negative urgency will be defined as a latent independent variable, with individual item indicators from the UPPS-P negative urgency subscale. Sensitivity to alcohol will be defined as a latent independent variable with three measured variable predictors: Subjective, behavioral and electrophysiological sensitivity to 60mg/dl alcohol as compared to each individual's baseline response. The dependent measures of interest for sensitivity analysis include Subjective Response to Alcohol, Wisconsin Card Sort, and the Stop Signal Task. The dependent variable will be cumulative work performed for alcohol in the aversive session, defined as an observed variable. We will control for cumulative work performed for alcohol in the neutral session, as well as age, gender, and race, due to their relationship with alcohol use behaviors. Judgment of hypothesis viability will be assessed via **1**) fit indices (recommendations in parentheses: Root Mean Square Error of Approximation ( $RMSEA < 0.10$ ); Tucker Lewis Index ( $TLI > 0.95$ ); and Comparative Fit Index ( $CFI > 0.95$ ) and **2**) pathway loading significance.

**Hypothesis 4:** Significant factors from hypothesis 3 can identify a latent trait that classifies individuals into at two classes of individuals: those who have high and low SDA. The significant phenotypes from hypothesis 3 will be used in a latent class analysis to identify subgroups based on

**Figure 6. Proposed path analysis.** Covariates, error terms, and correlations not shown for simplicity

their pattern of AUD risk. The Bayesian Information Criteria and entropy will be utilized to determine the number of latent classes that best fit the data. Individuals will be assigned to the latent class with the highest probability, and discrete class membership will be characterized using *post hoc* validators such as number of AUD criteria, negative urgency, family history density and lifetime drinking history. As a final validator, we will test if SDA is different between the classes to determine if class membership reflects motivation to work for alcohol in the face of aversive stimuli.

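### H3 relies on one structural equation model to limit error inflation, but this does not control the family-wise error over the five path tests: about 4.9% at 0.01 per path, 22.6% at 0.05

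*Combined protocol and SAP*

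**What the plan says.** All references are to the Statistical Considerations section of the combined protocol and SAP.

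- **Rationale (Aim 2 Hypothesis Testing Plan, H3).** The reason given for choosing structural equation modeling is "To minimize error inflation from multiple univariate tests".
- **Predictors.** The hypothesis begins "Those with greater SDA will have greater AUD severity, greater LDH, greater negative urgency, greater density of familial history of alcoholism, and reduced subjective, behavioral"; with the third form of sensitivity, the electrophysiologic one, it names seven phenotypes. The model reduces these. AUD symptom count, lifetime drinking history and family history density are observed variables, and negative urgency is a latent variable built from questionnaire items. The three sensitivity measures are combined: "Sensitivity to alcohol will be defined as a latent independent variable with three measured variable predictors". That leaves five structural paths to SDA. The model also adjusts for alcohol work in the neutral session, age, gender and race.
- **Decision rule.** "Judgment of hypothesis viability will be assessed via" two criteria: fit indices (RMSEA below 0.10, TLI and CFI above 0.95) and "pathway loading significance". No per-path alpha, multiplicity adjustment or joint test of the paths is given.
- **Downstream use (H4).** "The significant phenotypes from hypothesis 3 will be used in a latent class analysis".
- **Alpha elsewhere.** Power Analyses uses alpha 0.01 with power 0.90 for the AUD risk correlates (r = 0.32, n = 100). A threshold of 0.05 is stated only for the imaging analyses, H6a and H6b, where multiplicity measures are also described.

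**The concern.** Entering five predictors in one model adjusts each for the others. Each path still has its own test, and each test its own chance of a false positive. Nothing in the fitting step limits the chance that at least one of the five is wrong.

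The fit indices do not close the gap. RMSEA, TLI and CFI describe how well the model reproduces the observed covariances, and a model whose five structural paths are all zero can pass all three cut-offs.

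Two things are at stake. A reader may take the stated rationale as assurance that the H3 path results already allow for multiplicity. And H4 takes its inputs from the paths that reach significance, so a false path becomes an ingredient of the latent classes. With no alpha written down for H3, the threshold that decides which factors go forward is also left open.

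**Working it through.** **Inputs.** Five paths, counted from the H3 text. Completers: n = 100. Alpha 0.01, power 0.90, r = 0.32 and d = 0.64 with 50 per group, from Power Analyses. Alpha of 0.05 per path is an assumption, because H3 states none.

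**Step 1. Reproduce the plan's power, to see which alpha it implies.** For a correlation, power = Φ(atanh(r)·√(n−3) − z), with atanh(0.32)·√97 = 0.3316 × 9.849 = 3.266. For two groups with the normal approximation, power = Φ(d·√(50/2) − z), with 0.64 × 5 = 3.20.

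| Alpha | z | Power, r = 0.32 | Power, d = 0.64 |
|---|---|---|---|
| 0.01 two-sided | 2.576 | 75.5% | 73.4% |
| 0.01 one-sided | 2.326 | 82.6% | 80.9% |
| 0.05 two-sided | 1.960 | 90.4% | 89.3% |
| 0.05 one-sided | 1.645 | 94.8% | 94.0% |

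Using t distributions instead changes these by less than 2 percentage points. The stated 0.90 therefore agrees with two-sided 0.05 and not with the stated 0.01. At two-sided 0.01, 90% power would need 139 participants for r = 0.32, or 73 per group for d = 0.64.

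**Step 2. Family-wise error if all paths are null.** For k independent tests the rate is 1 − (1 − α)^k.

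| Per-path alpha | Seven separate tests | Five paths | Upper bound for five (5α) |
|---|---|---|---|
| 0.01 | 6.8% | 1 − 0.99^5 = 4.9% | 5% |
| 0.05 | 30.2% | 1 − 0.95^5 = 22.6% | 25% |

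Reducing seven tests to five lowers the rate. What remains depends on the per-path alpha.

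**Step 3. Does fitting the five jointly change this?** The simulation used a linear model with n = 100, five predictors and four covariates, no true predictor effects, predictor correlations of 0, 0.3, 0.5 and 0.7, and 20,000 runs per setting. At 0.05 per path the family-wise error was 21.9%, 22.2%, 21.2% and 21.0%. At 0.01 it was between 4.7% and 4.9% throughout. Joint fitting leaves the rate close to the independent-test value. The simulation uses observed-variable regression as a stand-in for the SEM, with no latent variables and no fit requirement.

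**Step 4. If some paths are real.** At 0.05 per path, with three null paths, 1 − 0.95^3 = 14.3%; with two, 1 − 0.95^2 = 9.8%.

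**The case against.** The strongest case for the plan has four parts.

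1. **The only alpha given for these relationships is 0.01.** Five tests at that level give 4.9%, which is Bonferroni at 0.05/5. If the 0.01 was meant for the H3 paths, control is already there. This limits the size of the problem but does not settle it: the 0.01 is not mentioned in H3, is not described as a multiplicity allowance, and does not agree with the power printed beside it.
2. **The text speaks of minimizing inflation, not of controlling an error rate, and the model does reduce the number of tests.** This stands. A reader might infer that SEM gives no protection at all. That goes too far, because the reduction from 30.2% to 22.6% at 0.05 is real, though partial.
3. **22.6% is close to a worst case.** This also stands. It needs 0.05 per path and every path null, whereas the plan's pilot correlations run from 0.32 to 0.63. All H3 paths have a predicted direction; counting only false results in that direction, two-sided 0.05 gives 1 − 0.975^5 = 11.9%. Requiring adequate fit as well cannot raise the rate.
4. **Harm to H4 is not demonstrated.** A false path would enter the latent class analysis, but the documents give no basis for saying how far one spurious indicator would alter the classes. The route is clear; its effect is not quantified.

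**Conclusion.** The point holds in a limited form. One SEM reduces the number of tests but does not control the family-wise error over the five paths that H3 judges by significance, and the fit indices do not supply that control. With all paths null, the chance of at least one false path runs from about 4.9% (0.01 per path) to about 22.6% (0.05 per path), and is lower if some paths are real. The documents do not settle which end applies: the stated alpha points to 0.01 and the stated power to two-sided 0.05.

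A reader might infer that the plan carries a false-positive risk of about 22%. The documents do not support that as an unconditional figure, because they never set 0.05 for H3.

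The result assumes five paths as the text describes them, since Figure 6 is not shown, and takes ordinary regression as a fair guide to the SEM path tests. This should be corrected before analysis. It does not undermine the design.

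**What to change.** In the Aim 2 Hypothesis Testing Plan:

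- State a family-wise alpha of 0.05 for H3 and apply Holm across the five path p-values, optionally after a nested-model chi-square test that all five are zero. The joint test should precede Holm, not replace it.
- Carry only the factors that remain significant after adjustment into the H4 latent class analysis.
- Reword the rationale to say that SEM reduces the number of tests but does not itself control the error rate.

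In Power Analyses, reconcile alpha and power. For r = 0.32 and n = 100, power is about 90% at two-sided 0.05 and about 76% at two-sided 0.01. The 50-per-group figure needs the same correction. If 0.01 per path was intended all along, saying so under H3 as 0.05/5 would also give control, with the power restated.

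**Cost.** One or two sentences, plus some power. The first Holm step tests at 0.05/5 = 0.01, so for the smallest pilot effect the loss is up to 90.4 − 75.5 = 14.9, about 15 points per path. Later Holm steps are less strict. These are powers for a simple correlation; power for an adjusted path in the SEM may differ.

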Our long-term goal is to use SDA as a platform for the laboratory testing of novel pharmacologic and behavioral interventions that can be used among those with the highest risk, but who have yet to progress to treatment-resistant drinking. The objective of this project is to test SDA across multiple levels of analysis. We consider SDA as an early marker of alcohol use disorder progression that is related to lifetime drinking history, alcohol use disorder risks, and brain physiology. Our current IARC pilot study (IRB #) demonstrates that SDA can be objectively quantified via an intravenous alcohol self-administration task, where operant work for identical incremental alcohol rewards is paired with aversive stimuli. Our preliminary data support our central hypothesis: that behavior in the SDA model is attributable to lifetime alcohol exposure, is related to alcohol use disorder (AUD) risk factors and phenotypes, and reflects alterations in neural system function. Specifically, they suggest that the degree of SDA is positively associated with recent drinking history, negative affect-based rash action (i.e. negative urgency, including action with respect to alcohol use), and self-rating of the effects of alcohol. The rationale for this work is that it would lead to the first objective, well-validated measure of SDA in humans.

Our specific aims are to:

*Aim 1:* Characterize SDA as a function of lifetime drinking history.

*Hypothesis 1:* Greater SDA will reflect greater lifetime drinking history.

*Hypothesis 2:* Those with a high lifetime drinking history will demonstrate less sensitivity to aversion in the preference to work for alcohol. Specifically, those with a high lifetime drinking history will work more for alcohol compared to water under both aversive and neutral experimental conditions, whereas those with a low lifetime drinking history will only work more for alcohol compared to water when alcohol seeking is paired with neutral stimuli.

Aim 2: Quantify associations between SDA and alcohol use disorder severity, and between SDA and risk phenotypes; then characterize how these risk factors classify individuals into those who will and will not work for alcohol in the context of aversive stimuli.

*Hypothesis 3:* Those with greater SDA will have greater AUD severity, greater negative urgency, a greater density of familial alcoholism, and reduced subjective, behavioral, and electrophysiologic sensitivity to alcohol.

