### Power Analyses

Alcohol self-administration: Our previous alcohol self-administration work showed effect sizes from 0.49 to 1.31 according to the phenotype of interest. Neurophysiological correlates (EEG/fMRI): Published outcome and feedback-related differences in N200 and P300 amplitudes yield effect sizes from 0.78 to 2.12 for subjects with an AUD versus controls, and 0.62 to 1.6 for the effect of alcohol. There are no standards for power analyses in whole brain connectomics. However, our pilot data showed significant results in  $n=51$ , suggesting  $n=100$  is sufficient to find robust connectivity patterns. We will ensure robustness using permutation tests combined with an extent threshold, or alternatively, using the Permutation Network Framework. Relationship to AUD risk variables: In our pilot data, the relationship between SDA and AUD risk correlates ranged from  $r=0.32 - 0.63$ . With a sample of  $n=100$ , we can detect an effect size of at least 0.32 and still maintain adequate  $power=0.90$ ,  $\alpha=0.01$ . When categorized by groups of  $n=50$  (high/low lifetime drinking history), we can detect differences with an effect size of 0.64 and still maintain adequate  $power=0.90$ ,  $\alpha=0.01$ .

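### Hypothesis 3 asks about the association of SDA with each phenotype, but is judged on mutually adjusted SEM paths that the power statement (r=0.32, n=100) does not cover

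*Combined protocol and SAP*

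**What the plan says.** Section 2.0 sets Aim 2 as: "Quantify associations between SDA and alcohol use disorder severity, and between SDA and risk phenotypes". Hypothesis 3 there reads "Those with greater SDA will have greater AUD severity, greater negative urgency, a greater density of familial alcoholism", and adds reduced sensitivity to alcohol. Section 7.0 repeats it with lifetime drinking history (LDH) added. Neither version says that each association must hold independently of the others.

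The Aim 2 testing plan in section 7.0 uses one joint model: "To minimize error inflation from multiple univariate tests, we will use structural equation modeling". On the outcome it says: "The dependent variable will be cumulative work performed for alcohol in the aversive session, defined as an observed variable". AUD symptom count, LDH, family-history density, latent negative urgency and latent sensitivity appear together. On covariates: "We will control for cumulative work performed for alcohol in the neutral session, as well as age, gender, and race". Hypothesis 3 is judged by fit indices and by "pathway loading significance". Hypothesis 4 builds its latent classes from the phenotypes that were significant under Hypothesis 3.

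The Power Analyses say "In our pilot data, the relationship between SDA and AUD risk correlates ranged from" 0.32 to 0.63, and claim power 0.90 at alpha 0.01 for an effect of 0.32 with n=100. They give no correlations among the phenotypes, no allowance for adjustment and no power for the SEM.

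**The concern.** A path in a joint model measures what a phenotype adds once the others are known. That is a different question from whether people with greater SDA have more of that phenotype. The protocol itself expects the phenotypes to travel together: section 2.0 attributes lower sensitivity to prolonged drinking, and Hypothesis 4 posits a latent trait behind them. A phenotype that is truly associated with SDA can then have a weak path of its own.

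Controlling for neutral-session alcohol work moves the target again. Hypothesis 1 defines SDA as work for alcohol in the aversive session, without that control.

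Two results are at stake: the verdict on each part of Hypothesis 3, and the choice of phenotypes that enter the latent class analysis. In addition, a reader of the Power Analyses would think the tests performed have power 0.90 at r=0.32, which has not been shown.

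**Working it through.** **Inputs from the documents.** n=100 completers (section 4.0); r=0.32 as the lowest pilot value, power 0.90 and alpha 0.01 (Power Analyses); five phenotypes plus neutral-session work, age, gender and race (Aim 2 testing plan).

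**Assumptions.** The documents do not give the inter-correlations, so I use a common value φ from 0 to 0.4. I read the pilot r as unadjusted, and reverse-score sensitivity so that all correlations are positive. Tests are two-sided. Observed-variable regression stands in for the SEM. Age, gender and race are taken to cost 3 degrees of freedom and nothing else.

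**Step 1: the plan's own figure.** Fisher z: power = Φ(atanh(r)·√(n−3) − z). Here atanh(0.32)·√97 = 3.266.
- Alpha 0.01: Φ(3.266 − 2.576) = 0.755 (one-sided: 0.826).
- Alpha 0.05: Φ(3.266 − 1.960) = 0.904.

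The stated 0.90 is reproduced at two-sided 0.05, not at the stated 0.01.

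**Step 2: one phenotype at a time, adjusted for age, gender and race.** Noncentrality δ = 0.32/√(1 − 0.32²) × √97 = 3.327, with 95 df. Noncentral-t power is 0.91 at alpha 0.05 and 0.76 at 0.01.

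**Step 3: five phenotypes mutually adjusted, without neutral-session work.** For equal r and equal φ:
- standardized path β = r/(1 + 4φ)
- R² = 5rβ
- variance inflation V = (1 + 3φ)/[(1 − φ)(1 + 4φ)]
- δ = β·√(97/[(1 − R²)V]), df = 100 − 5 − 3 − 1 = 91, critical values 1.986 and 2.631

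With r=0.32:

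| φ | β | R² | V | δ | Power, 0.05 | Power, 0.01 |
|---|---|---|---|---|---|---|
| 0 | 0.320 | 0.512 | 1.000 | 4.51 | 0.99 | 0.97 |
| 0.1 | 0.229 | 0.366 | 1.032 | 2.78 | 0.79 | 0.56 |
| 0.2 | 0.178 | 0.284 | 1.111 | 1.96 | 0.49 | 0.26 |
| 0.3 | 0.145 | 0.233 | 1.234 | 1.47 | 0.31 | 0.13 |
| 0.4 | 0.123 | 0.197 | 1.410 | 1.14 | 0.20 | 0.07 |

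A Fisher-z version on the partial correlation gives 0.75, 0.47, 0.29 and 0.19 at alpha 0.05 for φ = 0.1 to 0.4, so the approximation matters little.

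**Step 4: larger true correlations, φ=0.2, alpha 0.05.**
- All r=0.40: β = 0.222, R² = 0.444, δ = 2.79, power 0.79.
- All r=0.475 (middle of the pilot range): β = 0.264, R² = 0.627, δ = 4.04, power 0.98.

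**Step 5: unequal correlations.** Let the five r values be evenly spaced from 0.32 to 0.55. At φ=0.3 and alpha 0.05, the same calculation from the full correlation matrix gives power 0.06, 0.29, 0.67, 0.92 and 0.99, from weakest to strongest. At φ=0.1 the weakest has 0.91.

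**Step 6: adding neutral-session work.** All r=0.32, and neutral-session work correlates 0.6 with SDA (assumed). The test has 90 df and alpha is 0.05.
- Uncorrelated with the phenotypes, φ=0.1: partial correlation 0.395, power 0.99.
- Correlated 0.2 with each phenotype, φ=0.2: partial correlation 0.162, power 0.36.

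This control can therefore raise or lower power.

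**The case against.** The joint model is a deliberate choice, made to limit error inflation, and the wording of Hypothesis 3 can be read as a joint risk-factor model. Controlling for neutral-session work may be a sound way to isolate the effect of aversion. But judging several path p-values is still several tests. Joint modelling changes what each test asks; it does not by itself control their familywise error. The plan does not say that independent contribution is the intended question.

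Some protection exists. LDH has its own model under Hypothesis 1, without the other Hypothesis 3 phenotypes or neutral-session work. The latent classes are later compared on AUD criteria, urgency, family-history density and LDH, and on SDA. That protects LDH in part. It provides no direct test of SDA against AUD severity, urgency, family-history density or sensitivity.

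Figure 6 is not visible in the text reviewed, and LDH and family-history density are called observed rather than independent variables. Full five-way adjustment is thus the natural reading, but an inferred one.

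A reader might infer more than the documents support:
- That power simply falls from 0.91 to 0.2–0.5. This range needs r=0.32 throughout, φ of about 0.2 to 0.4 and alpha 0.05.
- That the stated power survives only if the phenotypes are uncorrelated. Steps 4 to 6 show correlated cases above 0.90.
- That the pilot range was borrowed from other variables. Section 2.0 does say that "the degree of SDA is positively associated with recent drinking history, negative affect-based rash action" and self-rated alcohol effects, but nothing says this list is the source of the range, and self-rated effects overlap with subjective sensitivity.

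**Conclusion.** The mismatch stands on the text alone: the hypothesis concerns each phenotype's association with SDA, the decision rests on mutually adjusted paths, and the power statement covers neither the adjustment nor the SEM. The consequence for power is conditional. With every true correlation at the bottom of the pilot range and moderate positive inter-correlation, power per path falls well below 0.90. With mid-range correlations and φ=0.2 it stays high at alpha 0.05. The documents do not show which case applies, so it does not follow that true associations will generally be missed. They could be, most readily for the weaker phenotypes, and a lost path would also alter the inputs to Hypothesis 4. Separately, 0.90 is already about 0.76 at the stated alpha of 0.01 before any adjustment. The point should be settled before analysis.

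**What to change.** In the Aim 2 testing plan, state which association Hypothesis 3 means. Add one model per phenotype, adjusted for age, gender and race, both with and without neutral-session alcohol work, and name in advance which of the two decides. Apply a step-down multiplicity adjustment. Use these models for the association statement and for choosing the phenotypes that enter Hypothesis 4. Report the joint SEM paths as evidence of independent contribution.

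In the Power Analyses, say that r=0.32 refers to the one-at-a-time tests, give its power at the alpha actually used (about 0.76 at 0.01), and add a range for the joint paths with its assumed inter-correlations.

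The cost is revised wording and a few extra models, with no new data. The multiplicity correction also has a price: with five tests at a familywise 0.05, the first step is 0.05/5 = 0.01, where one-at-a-time power at r=0.32 is about 0.76 rather than 0.91.

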*Hypothesis 4:* Significant factors from hypothesis 3 will identify a latent trait that classifies individuals into two types: those who have high SDA and those who have low SDA.

Aim 3: Identify signatures of neural function that underlie SDA.

*Hypothesis 5:* Those with greater SDA will demonstrate reduced event-related potential component amplitudes differences between negative vs. positive feedback about per-trial progress toward a reward. Those with greater SDA will demonstrate

*Hypothesis 6a:* greater resting state crosstalk between the default mode and fronto-parietal networks and *Hypothesis 6b:* reduced ventral striatal-ventromedial frontal connectivity.

The positive impact of this project will be to advance the translation between preclinical and clinical models and to elucidate distinct mechanisms underlying AUD progression in humans. Importantly, the proposed model uses objective behavior, rather than subjective symptom report. Our human component project is centered on the IARC theme and complements its preclinical components and methodologies. We expect that the results will facilitate the identification and evaluation of pharmacologic and behavioral interventions to minimize the risk of AUD progression risk in drinkers who have yet to manifest treatment resistant behavior.

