## **7.0 Statistical Considerations**

### **Aim 1: Characterize SDA across lifetime drinking history.**

#### Aim 1 Hypothesis Testing Plan

[figure not shown]
*Hypothesis 1: Greater SDA will reflect greater lifetime drinking.* We will conduct a linear mixed-model analysis, with lifetime drinking history as the continuous independent variable and with SDA as the dependent variable. Lifetime drinking history will be defined as the kg of alcohol reported consumed via the Concordia Lifetime Drinking Questionnaire. SDA will be defined as the amount of work performed (cumulative number of SDA trials completed) for alcohol rewards in the aversive session. Age, gender, recent drinking history, and race will be included as covariates, due to their relationship with AUDs.

**Hypothesis 2:** Those with a high lifetime drinking history will demonstrate less sensitivity to aversion in the preference to work for alcohol. Specifically, those with a high lifetime drinking history will work more for alcohol compared to water under both neutral and aversive conditions, whereas those with a low lifetime drinking history will only work more for alcohol compared to water in the neutral session. We will conduct a mixed linear model in which lifetime drinking history is the independent variable, as in hypothesis 1, but using a different dependent measure. We will subtract work for water from work for alcohol, dividing the difference by the sum of the work done for alcohol plus water (separately under the aversive stimulus ( $R_a$ ) and under the neutral stimulus ( $R_n$ )). The ratios  $R_a$  and  $R_n$  will be used as the repeated measures dependent variables, and lifetime drinking history (high vs. low), stimulus type (aversive vs. neutral) and their interaction will be independent variables. Covariates will include age, gender, recent drinking history, and race. If lifetime drinking history and the interaction with stimulus are significant predictors of the ratios of work performed, we will conduct follow-up planned contrasts to examine the ratios separately for the neutral and aversive sessions to test high and low lifetime drinking history.

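### Hypothesis 4 picks its class indicators by their link to SDA and then tests SDA between the classes, so once reached that p-value lacks its nominal error rate

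*Combined protocol and SAP*

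**What the plan says.** All references are to the combined protocol and SAP.

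- **Outcome.** Statistical Considerations, Aim 1, Hypothesis 1: "SDA will be defined as the amount of work performed (cumulative number of SDA trials completed) for alcohol rewards in the aversive session". The Hypothesis 3 model under Aim 2 has this same quantity as its dependent variable.
- **Adjustment in Hypothesis 3.** "We will control for cumulative work performed for alcohol in the neutral session", together with age, gender and race.
- **Selection rule.** Hypothesis 3 is judged by fit indices and by "pathway loading significance". No alpha is given for the latter.
- **Indicators in Hypothesis 4.** "The significant phenotypes from hypothesis 3 will be used in a latent class analysis to identify subgroups based on" their risk pattern. For the number of classes: "The Bayesian Information Criteria and entropy will be utilized to determine the number of latent classes that best fit the data". Each person goes to the most probable class.
- **Checks on the classes.** The plan profiles the classes on AUD criteria, negative urgency, family history density and lifetime drinking history (LDH). It then tests SDA between them as the closing check.
- **Claim to be supported.** Section 2.0: "Significant factors from hypothesis 3 will identify a latent trait that classifies individuals into two types".
- **LDH.** The Aim 2 analysis text of Hypothesis 3 includes it ("Those with greater SDA will have greater AUD severity, greater LDH, greater negative urgency"). The aims text in section 2.0 does not ("Those with greater SDA will have greater AUD severity, greater negative urgency, a greater density of familial alcoholism").

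**The concern.** A phenotype becomes a class indicator only because it tracked SDA in these data. Classes built from such indicators will tend to differ in SDA even if no phenotype is related to it, because the chance association that passed the filter carries through to the classes. The closing test then partly rediscovers the filter.

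At stake is how a small p-value is read. It would be taken as separate support for two types of drinker, when it largely restates Hypothesis 3. The descriptive validators have a related weakness: a measure that helped to form the classes must differ between them and so cannot validate them.

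**Working it through.** **Plan's own figure.** The plan gives no error rate or power for Hypothesis 4, so there is none to reproduce.

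**Inputs from the plan.** There are 100 completers (section 4.0). There are five candidate phenotypes in Hypothesis 3: AUD severity, LDH, negative urgency, family history density and sensitivity to alcohol. Hypothesis 3 adjusts for neutral-session work.

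**Assumed inputs.** Selection alpha is 0.05, or 0.01 because the Power Analyses use that value. The class test is at a nominal two-sided 5%. The correlation r between neutral and aversive work runs from 0 to 0.85. Regression stands in for the structural equation model. SDA is unrelated to all five phenotypes (global null).

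**Step 1: chance of reaching Hypothesis 4 under the null** (independent paths).
- Alpha 0.05: 1 - 0.95^5 = 0.226.
- Alpha 0.01: 1 - 0.99^5 = 0.049.

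**Step 2: share of those trials with exactly one indicator.**
- Alpha 0.05: 5 × 0.05 × 0.95^4 / 0.226 = 0.90.
- Alpha 0.01: 5 × 0.01 × 0.99^4 / 0.049 = 0.98.

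**Step 3: hand calculation for one normal indicator split in two at its median.** Let Z be the Hypothesis 3 statistic and W the unadjusted class-SDA statistic. Under the null they are approximately bivariate standard normal. A median split keeps a correlation of √(2/π) = 0.798 with the indicator, and neutral work dilutes it, so corr(Z, W) = 0.798 × √(1 - r²). This gives 0.798, 0.691, 0.570 and 0.420 at r = 0, 0.5, 0.7 and 0.85. The rejection rate is P(|W| > 1.96 given |Z| > c), with c = 1.960 (alpha 0.05) or 2.576 (alpha 0.01).

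**Step 4: simulation.** Normal and skewed indicators were used, with and without correlation with the LDH bands and discretionary enrolment. A two-class Gaussian mixture was imposed and the SDA test was unadjusted, with 24,000 null trials per setting.

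| r | 0.05: hand | 0.05: simulated | 0.01: hand | 0.01: simulated |
|---|---|---|---|---|
| 0 | 0.44 | 0.31-0.48 | 0.70 | 0.48-0.74 |
| 0.5 | 0.32 | 0.25-0.36 | 0.52 | 0.38-0.56 |
| 0.7 | 0.23 | 0.18-0.25 | 0.35 | 0.26-0.36 |
| 0.85 | 0.14 | 0.12-0.15 | 0.21 | 0.15-0.22 |

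The nominal value is 0.05 throughout. The inflation is smallest when the two sessions' work is highly correlated and the test is unadjusted. If the test keeps neutral work as a covariate, the dilution disappears and the hand figure is 0.44 or 0.70 whatever r is.

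**Step 5: rate over all null trials** (Step 1 × Step 3).
- Alpha 0.05: 0.226 × 0.14 = 0.03 to 0.226 × 0.44 = 0.10. Simulated: 2.5-10.5%.
- Alpha 0.01: 0.049 × 0.21 = 0.01 to 0.049 × 0.70 = 0.03. Simulated: 0.7-3.7%.

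**Step 6: controls.** With all five indicators fixed in advance, rejection was 0.047-0.053. With selection in one sample and classification and testing in another, it was 0.060 (mixture) and 0.049 (median split), Monte Carlo standard error about 0.005. The inflation therefore comes from selecting and testing on the same data.

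**The case against.** **Most of the null trials are an odd case.** By Step 2, about nine in ten select one indicator, whereas the plan speaks of several phenotypes forming a pattern. This stands as a limit on the size. With two or more indicators at selection 0.05, rejection was still about 11-31%, from small counts. If two or more are required, Hypothesis 4 is reached in about 3% of null trials, and selection plus rejection occurs in 0.4-0.9% of all trials. At 0.01 such trials were too few to give a rate.

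**The global null may be remote.** The Power Analyses report pilot correlations of 0.32 to 0.63 between SDA and risk measures. If a selected phenotype truly relates to SDA, a class difference is generally real. The fault is then redundancy with Hypothesis 3, not a false positive.

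**The comparison may be meant as description.** The plan sets no alpha for it. However, it is worded as a test and as the last validation of the classes, so a reader will take the p-value at face value.

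**The model is simplified.** The fit-index criteria, the latent measurement models and entropy were not simulated. That affects the size and the chance of reaching the test, not the direction.

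**Stronger readings the documents do not support.** A reader might infer that Hypothesis 4 yields a false positive in up to half of null studies; Step 5 shows otherwise, because few null trials reach the test. A reader might also infer that LDH's role is contradictory. The analysis text includes it and the aims text omits it, which is a wording mismatch. The path diagram, not available here, may settle it.

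**Conclusion.** The point holds in a limited form. Selection and test use the same variable and, by inference, the same completers; the plan names no other sample but does not state the analysis set either. Once Hypothesis 4 is reached, the class-SDA p-value lacks its nominal error rate and cannot confirm anything beyond Hypothesis 3.

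Under a global null, a nominal 5% test with two classes imposed rejects in roughly 10-50% of the trials that reach it at selection alpha 0.05, and in more at 0.01. Over all null trials the rate is about 1-10%. These sizes rest on the assumed correlations, the assumed alphas and regression in place of the structural equation model. Confidence is high for the direction only. The point affects how one Aim 2 hypothesis is interpreted.

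**What to change.** Choose one of these in the SAP:

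1. Report the class-SDA comparison as descriptive, and do not present it as validating two types.
2. Keep the test, and take its p-value from permutation. Shuffle each participant's aversive and neutral work together, rerun selection, classification and test each time, and compare only with permutations that reach the test. The selection alpha and any adjustment for neutral work must be fixed for this to be run. In simulation this rejected in 0.046 of 3,594 null trials that reached the test (0.020-0.063 across 12 settings of about 300 trials), where the uncorrected p-value rejected in 0.22-0.62.

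In both cases:

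- Do not count as a validator any measure that served as a class indicator.
- If LDH is an indicator, cross-tabulate the classes against the recruited bands (25-50 kg and 250-500 kg). Do not read a solution that reproduces the bands as two natural types.

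Fixing all Hypothesis 3 phenotypes as indicators in advance also restores the error rate, but it is not the lead fix. It changes Hypothesis 4, and it may return the recruitment bands or a single class. In simulation with LDH included and normal or moderately skewed indicators, two-class solutions matched the bands for 99-100% of banded participants. Without LDH, normal indicators gave one class every time.

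The cost is SAP wording and a little computing for the permutation, or a weaker claim for Hypothesis 4 if the comparison becomes descriptive. No new data are needed.
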